1.1 Study Objectives

1.1.1 Primary Objectives

The primary objective is to evaluate the efficacy of mepolizumab initiated during hospitalisation on future hospital readmission or death (all cause) compared with placebo in severe exacerbations of eosinophilic COPD.

1.1.2 Secondary Objectives

To assess the effects of mepolizumab on health status, well-being, exercise capacity, frailty, moderate exacerbations, healthcare usage, and death, compared with placebo in patients admitted to hospital with an eosinophilic exacerbation of COPD.

1.1.3 Subgroup Objectives

To evaluate if the efficacy, in terms of the primary outcome, is different between grouped baseline stratification factors of 1) MRC dyspnoea score (≤ 3 , > 3) and 2) past hospitalisation in the previous 12 months (0 , ≥ 1) and WHO clinical progression score at baseline (4, 5, 6).

2 Study Design

This will be a single-centre, double-blinded, randomised, placebo-controlled trial comparing mepolizumab 100mg versus placebo in patients with eosinophilic COPD, started during their index admission to hospital. 238 participants will be recruited over a 3-year period.

Participants will be dosed every 4 weeks for 48 weeks and be followed up for 12 months with the exception of those randomised during the truncated follow-up period.

2.1 *Truncated follow-up*

Patients randomised from July 2023 to December 2023 will be consented to a truncated follow-up model, whereby the timing of the last patient last visit will remain on the same timeline as originally planned; this will result in participants consented in July to have up to the 44-week follow-up, those in August will have up to the 40-week follow-up, and so on. Patients will be dosed for a minimum of 20 weeks, with secondary outcomes measured as per original timelines (baseline, 4 weeks, 8 weeks, etc.) however final outcome measures normally measured at 48 weeks will occur at 4 weeks \pm 7 days post final dosing visit.

2.2 Overview

2.2.1 Participants

Adults aged 40 years old and above with symptoms typical of COPD when stable (baseline eMRC dyspnoea grade 2 or more) and whose Serum Eosinophil count is ≥ 300 cells/ μ L either at time of admission or at any one time in the preceding 12 months will be deemed as eligible participants. However, COPD adults without eosinophilia (defined as persistently < 300 cells/ μ L within the last 12 months) and who have other conditions that may be the cause of eosinophilia would make any potential participant ineligible to take part in the Study.

2.2.2 Treatment groups

Participants will be randomised in a 1:1 ratio to mepolizumab or placebo.

2.2.2.1 Mepolizumab group

The Investigational Medicinal Product (IMP) for this trial is mepolizumab 100mg powder for solution for injection.

Dosing will be undertaken every four weeks (\pm 7 days) over 48 weeks (12 doses in total), each consisting of 100mg of mepolizumab or placebo, administered subcutaneously. Participants are required to complete the scheduled clinic visits within the specified time windows in order to maintain sufficient intervals between

doses. Trial medication can only be administered at the Respiratory BRC. The participant will return on an outpatient basis following their initial hospitalisation every four weeks to receive their scheduled dose and undertake trial assessments. For participants who do not receive dosing during their index hospitalisation, the first injection must occur within seven days of discharge. The participant's time in the trial begins at randomisation.

Scheduled doses can be delayed by up to four weeks. The exception will be if dosing is delayed due to an exacerbation resulting in hospitalisation, where there will be no limit on the length of delay, and the next dose will be administered at the next due date or as soon as possible afterwards to allow the participant to recover. A delay will then be carried through to all their subsequent study visits. If the participant misses a dose it will be recorded in the medical notes and the next scheduled dose will be administered. Participants will be allowed to miss one dose of the study drug only, or they will be discontinued from the trial treatment. Dosing completed outside of the seven day window will be recorded as a protocol deviation.

Participants consented to the truncated follow-up phase of the study will follow the dosing regimen of one dose every 4 weeks (± 7 days) for at least 20 weeks (minimum of 6 doses); however the number of doses will be dependent on when they consented to the study i.e. patients consented earlier will receive more. The method of dosage and blinding procedures will remain the same.

2.2.2.2 Placebo group

Dosing will be undertaken every four weeks (± 7 days) over 48 weeks (12 doses in total), each consisting of 100mg of mepolizumab or placebo, administered subcutaneously. Participants are required to complete the scheduled clinic visits within the specified time windows in order to maintain sufficient intervals between doses. Trial medication can only be administered at the Respiratory BRC. The participant will return on an outpatient basis following their initial hospitalisation every four weeks to receive their scheduled dose and undertake trial assessments. For participants who do not receive dosing during their index hospitalisation, the first injection must occur within seven days of discharge. The participant's time in the trial begins at randomisation.

Scheduled doses can be delayed by up to four weeks. The exception will be if dosing is delayed due to an exacerbation resulting in hospitalisation, where there will be no limit on the length of delay, and the next dose will be administered at the next due date or as soon as possible afterwards to allow the participant to recover. A delay will then be carried through to all their subsequent study visits. If the participant misses a dose it will be recorded in the medical notes and the next scheduled dose will be administered. Participants will be allowed to miss one dose of the study drug

only, or they will be discontinued from the trial treatment. Dosing completed outside of the seven day window will be recorded as a protocol deviation.

Participants consented to the truncated follow-up phase of the study will follow the dosing regimen of one dose every 4 weeks (± 7 days) for at least 20 weeks (minimum of 6 doses); however the number of doses will be dependent on when they consented to the study i.e. patients consented earlier will receive more. The method of dosage and blinding procedures will remain the same.

2.2.3 Sample size

Readmission rates at 6, 9 and 12 months were 51%, 59% and 64% respectively for patients admitted with a diagnosis of COPD (ICD code: J44) in Leicestershire in 2015. This is in line with national data from the HQIP RCP National COPD audit (2014) which had a readmission rate of 43% at 3 months. In addition, 6% of patients discharged from hospital with an exacerbation of COPD died in the 12 months following admission without hospital readmission.

National UK data from the HQIP funded RCP/BTS National COPD audit (2014; data unpublished) showed 24.9% patients had an eosinophil count of ≥ 300 cells/ μL on admission. In patients with an eosinophil of ≥ 300 cells/ μL on admission ($n=1,587$), 46.1% of patients were readmitted within 3 months of initial hospitalisation, similar to the non-eosinophilic COPD population.

Assuming 65% of patients receiving usual care will have an event by 48 weeks (composite endpoint: hospitalisation or death) and those treated with mepolizumab have a hazard ratio of 0.6, then 226 patients (113 per group) would be required to show a statistical difference power 0.8, $\alpha=0.05$). We have also assumed 5% drop-out (recruited but not receiving first dose) and therefore the final recruitment target of 238 patients.

2.2.4 Randomisation and blinding

The LCTU will supply a web based randomisation system from a third party (Sealed Envelope Ltd.). Participants will be randomised in a 1:1 ratio to mepolizumab or placebo. The trial team and participants will be blinded to treatment assignment. Randomisation will be stratified on baseline eMRC dyspnoea score (≤ 3 , >3) and past hospitalisation in the previous 12 months (0, ≥ 1).

Each participant will be given a unique trial ID number at randomisation. Randomisation results will be printed out and signed as confirmation by the unblinded trial personnel performing the randomisation and a copy will be stored securely with the unblinded documentation and presented to pharmacy alongside the prescription.

[.....]

Participants, investigators, and all involved in trial conduct, sample analysis, or with any other interest in this trial will remain blind to the randomised treatment assignments until after final analysis is complete. The exception(s) to this are as follows;

- The trial statistician will have access to the web based randomisation database of all randomised participants in order to prepare the unblinded DMC to make safety decisions and complete end of trial analyses.
- The Pharmacy team will be unblinded and have responsibility for storing and dispensing IMP and placebo.
- Unblinded trial personnel from the Respiratory BRC will have responsibility for reconstituting the IMP/placebo and dosing the participants.

[.....]

The treatment allocation will remain blinded to all other trial team members until after database lock.

2.2.5 Emergency Unblinding

[.....]

Unblinding will only occur in the case of a medical emergency when the identity of the allocated treatment must be known in order to provide appropriate medical treatment. It is not anticipated that unblinding will be required in this trial as there is no recovery treatment.

[.....]

Unblinding of all participants will be undertaken by the trial statistician after the last participant has completed their final visit, and the database has been locked.

2.3 Visit schedule

Trial assessment	Randomised treatment (visit window +/- 7 days)												
	V1	V2	V3	V4	V5	V6	V7	V8	V9	V 10	V 11	V 12	V 13/Final follow up
	Wk0	Wk4	Wk8	Wk12	Wk16	Wk20	Wk24	Wk28	Wk32	Wk36	Wk40	Wk44	Wk48
Consent	x												
Review Inclusion & Exclusion	x												
Randomisation	x												
Dosing	x	x	x	x	x	x	x	x	x	x	x	x	
Demographics, medical history & physical exam	x												
Concomitant Med	x	x	x	x	x	x	x	x	x	x	x	x	x
Vital signs	x	x	x	x	x	x	x	x	x	x	x	x	x
Blood serum pregnancy test (if applicable)	x												
Urine Pregnancy test (if applicable)		x	x	x	x	x	x	x	x	x	x	x	x
Electrocardiogram (ECG ^f), Chest X-ray (CXR ^s), Arterial blood gas (ABG) (part of standard care), spirometry [^] (FEV1, FVC, FEV1 % predicted)	x												
WHO Clinical Progression Score	x												
Extended MRC dyspnoea score (eMRC)*	X*	x	x	x			x			x			x
St George's Respiratory Questionnaire (SGRQ)	x	x	x	x			x			x			x
COPD Assessment Tool (CAT)	x	x	x	x			x			x			x

Warwick-Edinburgh Mental wellbeing score (WEMWBS)	x	x	x	x			x			x			x
London Chest Activities of Daily Living Questionnaire (LCADL)	x	x	x	x			x			x			x
Short physical performance battery (SPPB)	x	x	x	x			x			x			x
Physical activity (accelerometry)	x	x	x	x			x			x			
Handgrip strength	x	x	x	x			x			x			x
Inflammatory markers (serum & sputum [#] samples)	x	x	x	x			x			x			x
Safety and tolerability AE/SAEs and bloods (FBC, U&E, LFTs, CRP)	x	x	x	x	x	x	x	x	x	x	x	x	x
Sputum inflammatory differential	x	x	x	x			x			x			x
Sputum [#] sample (sputum microbiome, systemic inflammation)	x	x	x	x			x			x			x
Exploratory blood samples (Trop I, BNP, FBC, serum & plasma)	x	x	x	x			x			x			x
Exploratory urine sample	x	x	x	x			x			x			x
Quadriceps ultrasound	x	x	x	x			x			x			x
Immunophenotyping & Microbiology samples (blood, sputum [#] , urine)	x	x	x	x			x			x			x

[£] 12 lead ECG, done as part of the standard clinical care. If, in the opinion of investigator, the ECG is grossly abnormal (e.g. LBBB, prolonged QTc), it will be compared to old ECGs. If there are no old ECGs for comparison, the investigator will make a clinical judgement about the suitability of the patients to take part in trial.

[§] Chest X-ray: done as part of routine clinical care during acute admission. [^]Results from historical or contemporaneous spirometry testing performed as part of usual care will be collected from hospital and primary care records where available. ^{*}Two eMRC dyspnoea scores will be recorded at visit 1 only (current and baseline/stable states). [#]Spontaneous sputum samples collected as part of standard of care.

Note: Trial assessments (e.g. Quality of Life/Symptoms Assessments) may be completed remotely by telephone consultation where possible and when necessary.

Additional note: Patients consented to truncated follow-up will follow schedule of procedures as defined in this table up until their final dosing visit whereby V13/Final Follow-up will then occur 4 weeks ±7 days later.

3 Outcomes and other variables

3.1 Primary Outcome

3.1.1 Definition and Derivation of Primary Outcome

Time from randomisation to next hospital readmission or death (all cause).

The time from randomisation to next hospital readmission or death (all cause) is defined as a time to event outcome measured in days. The date of randomisation as well as the date of readmission or death (whichever occurs first) will be used to calculate time to event. For participants not experiencing an event the time will be calculated from randomisation until last known follow-up assessment event-free. A variable to indicate event (with a value of 1) or no event (with a value of 0) will be derived. Details of the primary outcome analysis are included in section 5.5.

3.1.2 Hypothesis to be investigated

To evaluate the efficacy of mepolizumab initiated during hospitalisation on future hospital readmission or death (all cause) compared with placebo in severe exacerbations of eosinophilic COPD.

3.2 Secondary Outcomes

3.2.1 Definition and Derivation of Secondary Outcomes

Exacerbations and Healthcare Utilisation

- Time from randomisation to next hospital readmission or death due to a respiratory cause

The time from randomisation to next hospital readmission or death (due to a respiratory cause) is defined as a time to event outcome measured in days. The date of randomisation as well as the date of readmission or death due to respiratory causes (whichever occurs first) will be used to calculate time to event. For participants not experiencing an event the time will be calculated from randomisation until last known follow-up assessment event-free. A variable to indicate event (with a value of 1) or no event (with a value of 0) will be derived. Details of the primary outcome analysis are included in section 5.5.

- Total number of hospital readmissions all cause up to 48 weeks

The total number of hospital readmissions (all cause) is defined as a count outcome. The number of hospital readmissions (all cause) in total during the 48 (truncated follow-up

minimum 24) weeks corresponding to each participant will be calculated. Where no hospital admission have occurred a value of zero will be derived.

- Total number of moderate exacerbations up to 48 weeks

The total number of moderate exacerbations is defined as a count outcome. The severity of a COPD exacerbation will be deemed as “Moderate” if the participant required treatment with steroids or antibiotics and was not hospitalised (Oba, Y. et al, 2017).

The number of moderate exacerbations each participant had over the course of 48 (truncated follow-up minimum 24) weeks will be calculated.

- Time from randomisation to treatment failure (defined as the composite of three endpoints: 1. treatment intensification with systemic corticosteroids and/or antibiotics for respiratory reasons; 2. step-up in hospital care for respiratory reasons including transfer to the intensive care unit or readmission; or 3. all-cause mortality)

The time from randomisation to treatment failure is defined as a time to event outcome measured in days. The date of randomisation and dates of treatment intensification and increase in hospital care (whichever is the latter) will be used to calculate time to event. Participants not experiencing both treatment intensification and increased hospital care will have time measured from randomisation until last known follow-up assessment event-free. A variable to indicate event (with a value of 1) or no event (with a value of 0) will be derived.

- Time from randomisation to death (all cause)

The time from randomisation to death (all cause) is defined as a time to event outcome measured in days. The date of randomisation and the date of death will be used to calculate time to event. For participants with no known death date the time will be calculated from randomisation until last known follow-up assessment. A variable to indicate event (with a value of 1) or no event (with a value of 0) will be derived.

- Time from randomisation to death (respiratory cause)

The time from randomisation to death (respiratory cause) is defined as a time to event outcome measured in days. The date of randomisation and the date of death where cause is defined as respiratory will be used to calculate time to event. For participants with no known death date the time will be calculated from randomisation until last known follow-up assessment. For participants with a date of death attributed to other (non-respiratory) causes the time will be calculated from randomisation until death. A variable to indicate event (with a value of 1) or no event (with a value of 0) will be derived.

- Time from randomisation to next hospital readmission (all cause)

The time from randomisation to next hospital readmission (all cause) is defined as a time to event outcome measured in days. The date of randomisation and the date of next hospital readmission following randomisation will be used to calculate time to event. Where hospital readmission doesn't occur during follow-up, time will be measured until the participant's last known follow-up assessment. A variable to indicate event (with a value of 1) or no event (with a value of 0) will be derived.

- Time from randomisation to next hospital readmission (respiratory cause)

The time from randomisation to next hospital readmission (respiratory cause) is defined as a time to event outcome measured in days. The date of randomisation and the date of next hospital readmission (respiratory cause) will be used to calculate time to event. Where hospital readmission for respiratory cause doesn't occur during follow-up, time will be measured until the participant's last known follow-up assessment. A variable to indicate event (with a value of 1) or no event (with a value of 0) will be derived.

- Time to discharge from index admission

Time to discharge from index admission is a continuous outcome defined as the time (measured in days) from index admission to discharge. The date of index admission and the date of hospital discharge will be used to calculate length in days and the resulting index admission duration, expressed in days, will be incorporated into the baseline characteristics for analysis and reporting. Participants with a date of death and no discharge date will not have a value for length of index admission and therefore not included in the analysis of this outcome measure.

Quality of Life/Symptoms (Weeks 0, 4, 8, 12, 24, 36, 48*)

*See section 1.2 – Truncated follow-up; Participants randomised from June 2023 will receive minimum 24 weeks follow-up.

- Breathlessness:
 - Extended MRC dyspnoea score (eMRC)

The extended MRC dyspnoea scale is defined as an ordinal outcome. It consists of five statements about a perceived grade of breathlessness related to activity, with the grades defined as shown below:

- Grade 1: Breathless only with strenuous exercise.
- Grade 2: Breathless when hurrying on the level or walking up a slight hill.
- Grade 3: Walks slower than peers or stops when walking on the flat at own pace.
- Grade 4: Stops after walking 100m, or for a few minutes, on the level.
- Grade 5: Too breathless to leave the house.

For participants who perceive themselves to be in a Grade 5 on the traditional MRCD scale, the eMRCD will categorise them as either 5a or 5b depending on their ability to manage personal care (i.e. washing and dressing) (Nerys, W.,2017; Steer J. et al, 2011).

The baseline value used in analysis should be the stable state value captured at baseline post randomisation, the actually value taken at baseline during the exacerbated state is for describing baseline characteristics only.

- Health Status
 - St George's Respiratory Questionnaire (SGRQ)
 - COPD Assessment Tool (CAT)

The St George's Respiratory Questionnaire (SGRQ-C COPD specific) score is defined as a continuous outcome. There are two parts to the questionnaire providing a total of 3 component scores (or subscales) as below;

- Part 1: Symptoms (8 items).
- Part 2: Activity (16 items)
- Part 2: Impacts (26 items).

Each questionnaire response has a unique empirically derived 'weight'. The lowest possible weight is zero and the highest is 100. A Total and three component scores are calculated: Symptoms; Activity; Impacts.

The Symptoms component consists of all the questions in Part 1. The weights for Questions 1-7 are summed.

The Activity component is calculated from the summed weights for the positive responses to items Questions 9 and 12 in Part 2 of the questionnaire.

The Impacts component is calculated from Questions 8, 10, 11, 13, 14 in Part 2 of the questionnaire.

Then the Total score is calculated by summing the weights to all the positive responses in each component.

For each subscale and the total score, values range from 0 (no impairment) to 100 (maximum impairment) (Ferrer M. et al, 2002).

The COPD Assessment Tool (CAT) score is defined as a continuous outcome that ranges from 0 to 40 (inclusive) higher scores indicating a more severe health status impairment or a poorer control of COPD. It consists of eight items, with each item presented as a 6-point (0 to 5) differential scale, providing a score out of 40 indicating the clinical impact of the disease.

- Mental wellbeing
 - Warwick-Edinburgh Mental wellbeing score (WEMWBS)

The Warwick-Edinburgh Mental wellbeing score is defined as a continuous outcome that ranges from 14 to 70 (inclusive). The Questionnaire consists of 14 items with each item using a 5-point Likert scale: 1 ("None of the time"), 2 ("Rarely"), 3 ("Some of the time"), 4 ("Often") and 5 ("All of the time"). The total score sums all 14 items with higher scores indicating a higher level of mental wellbeing (Tennant R. et al, 2007).

- Functional
 - London Chest Activities of Daily Living Questionnaire (LCADL)

The London Chest Activities of Daily Living is defined as a continuous outcome that measures the limitation to perform activities of daily living by dyspnoea. It comprises 15 questions which are divided into four domains: self-care, household activities, physical activity and leisure activities. The questions in each of the four domains are scored as follows: 0 ("I wouldn't do it anyway"), 1 ("I do not get breathless"), 2 ("I get moderately breathless"), 3 ("I get very breathless"), 4 ("I have given this up") and 5 ("Someone else does this for me"). The LCADL total score sums all individual questions to give values in the range 0 to 75 (inclusive), with the highest score representing maximal disability (Muller, J. P. et al, 2013; Garrod, R. et al, 2000).

Physiological Measures (Weeks 0, 4, 8, 12, 24, 36, 48*)

*See section 1.2 – Truncated follow-up; Participants randomised from June 2023 will receive minimum 284 weeks follow-up.

- Frailty
 - Short physical performance battery (SPPB)
 - Handgrip Strength

The Short physical performance battery is defined as a continuous outcome that ranges from 0 (worst performance) to 12 (best performance) (Pavasini, R. et al, 2016). This outcome measures lower extremity function using tasks that are similar to daily activities and it examines 3 areas: static balance, gait speed and getting in and out of a chair. The limitations based on the SPPB cut-off scores are defined as follows: "Severe limitations" if score is between 0-3, "Moderate limitations" if score is between 4-6, "Mild limitations" if score is between 7-9 and "Minimal limitations" if score is between 10-12 (Puthoff M.L., 2008).

This secondary outcome will be derived as a categorical variable for descriptive statistics purposes.

Handgrip strength is defined as a continuous outcome that measures the amount of static force that the hand can squeeze around a dynamometer. This outcome is measured in Kilograms (Massy-Westropp N.M. et al, 2011).

*Values will be rounded to one decimal place.

Inflammatory Markers (Weeks 0, 4, 8, 12, 24, 36, 48*)

*See section 1.2 – Truncated follow-up; Participants randomised from June 2023 will receive minimum 24 weeks follow-up.

- Serum eosinophil count (total count)

The serum eosinophil count is defined as a continuous outcome that is measured in cells/mL. Values are rounded to two decimal places.

- Sputum eosinophil count (percentage)

The sputum eosinophil count (percentage) is defined as a continuous outcome that is expressed as a percentage (Belda, J. et al, 2000). Values are rounded to one decimal place.

Safety and Tolerability (all visits)

- AE event rate per year in the 48 weeks of the trial from first dose
- SAE event rate per year in the 48 weeks of the trial from first dose

The number of adverse and serious adverse events is defined as a count variable. Furthermore, AE and SAE event rates will be reported as incidence rates per person years and calculated as (total number of events / sum of all follow-up times) *52 where;

-Total number of events is a count of all AE/SAEs observed.

-Follow-up time is calculated per participant from time of first dose until the last trial assessment is recorded.

- Clinical assessments and investigations (heart rate, blood pressure, temperature)

Heart rate, blood pressure and temperature are defined as continuous outcomes that are measured in bpm, mmHg and °C, respectively. Temperature values are rounded to one decimal place.

Exploratory Outcome Measures

- Physical Activity using accelerometry (Weeks 0, 4, 8, 12, 24, 36, 48*)

The analysis of physical activity accelerometer data from GeneActive will be treated as an exploratory analysis and will be conducted independently outside the scope of this Statistical Analysis Plan (SAP).

*See section 1.2 – Truncated follow-up; Participants randomised from June 2023 will receive minimum 24 weeks follow-up.

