3.3.2. Secondary Outcome Measures

3.3.2.1. Exacerbations and Healthcare Utilisation

- Time from randomisation to next hospital readmission or death due to a respiratory cause
- Total number of hospital readmissions all cause up to 48 weeks
- Total number of moderate exacerbations up to 48 weeks
- Time from randomisation to treatment failure (defined as the composite of three endpoints: 1. treatment intensification with systemic corticosteroids and/or antibiotics for respiratory reasons; 2. step-up in hospital care for respiratory reasons including transfer to the intensive care unit or readmission; or 3. all-cause mortality)
- Time from randomisation to death (all cause)
- Time from randomisation to death (respiratory cause)
- Time from randomisation to next hospital readmission (all cause)
- Time from randomisation to next hospital readmission (respiratory cause)
- Time to discharge from randomisation

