10 STATISTICS AND DATA ANALYSIS

10.1 Sample size calculation

Readmission rates at 6, 9 and 12 months were 51%, 59% and 64% respectively for patients admitted with a diagnosis of COPD (ICD code: J44) in Leicestershire in 2015. This is in line with national data from the HQIP RCP National COPD audit (2014) which had a readmission rate of 43% at 3 months. In addition, 6% of patients discharged from hospital with an exacerbation of COPD died in the 12 months following admission without hospital readmission.

National UK data from the HQIP funded RCP/BTS National COPD audit (2014; data unpublished) showed 24.9% patients had an eosinophil count of ≥ 300 cells/ μL on admission. In patients with an eosinophil of ≥ 300 cells/ μL on admission ($n=1,587$), 46.1% of patients were readmitted within 3 months of initial hospitalisation, similar to the non-eosinophilic COPD population.

Assuming 65% of patients receiving usual care will have an event by 48 weeks (composite endpoint: hospitalisation or death) and those treated with mepolizumab have a hazard ratio of 0.6, then 226 patients (113 per group) would be required to show a statistical difference power 0.8, $\alpha=0.05$). We have also assumed 5% drop-out (recruited but not receiving first dose) and therefore the final recruitment target of 238 patients.

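### The SAP derives treatment failure as intensification and step-up together, at the later date and without death, whereas the protocol counts any one of three components

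*SAP*

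**What the plan says.** Protocol 3.3.2.1 lists time to treatment failure as a secondary outcome, "defined as the composite of three endpoints: 1. treatment intensification with systemic corticosteroids and/or antibiotics for respiratory reasons", with a second component of respiratory step-up in hospital care, "including transfer to the intensive care unit or readmission; or 3. all-cause mortality". The components are joined by *or*, so any one of them is a failure. The bullet in SAP 3.2.1 gives the same three-part definition.

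The derivation paragraph under that bullet does something else. On the event date, the "dates of treatment intensification and increase in hospital care (whichever is the latter) will be used to calculate time to event". On non-events, "Participants not experiencing both treatment intensification and increased hospital care will have time measured from randomisation until last known follow-up assessment event-free". Death is not mentioned in that paragraph.

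For the primary composite the same SAP uses the usual rule: the date of readmission or death, "whichever occurs first) will be used to calculate time to event" (SAP 3.1.1). SAP 6.8 lists no changes to the planned analysis.

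**The concern.** The derivation departs from the definition in three ways.

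- **Logic.** It needs both non-fatal components where the definition needs any one of three.
- **Date.** It uses the later date where a time-to-first-event composite uses the earliest.
- **Death.** It drops all-cause mortality.

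Two groups are misclassified outright. Participants whose only events are moderate exacerbations, which SAP 3.2.1 defines as steroid or antibiotic treatment without hospitalisation, have intensification but no readmission. They become non-events. Protocol section 1 cites fewer moderate exacerbations as the existing COPD evidence for mepolizumab, so the rule discards much of the component where an effect has been reported. Participants who die without both other components are coded 0 and censored. Those who do have both components are dated late unless the two coincide.

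A hazard ratio computed this way would be reported as treatment failure but could not be read as the protocol's endpoint. If the conflict is left until the analysis, someone must choose between two rules after database lock, and a SAP exists to remove that choice.

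**Working it through.** **1. The plan's own figure.** The documents give no event rate or power for treatment failure. The only sample size is for the primary outcome (Protocol 10.1): "Assuming 65% of patients receiving usual care will have an event by 48 weeks" and "those treated with mepolizumab have a hazard ratio of 0.6", power 0.8, alpha 0.05.

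- Freedman events, two-sided: (1.96 + 0.84)² × [(1 + 0.6)/(1 − 0.6)]² = 7.85 × 16 = 125.6, so 126.
- Event probability on mepolizumab: 1 − 0.35^0.6 = 0.467. Mean of the two arms: (0.65 + 0.467)/2 = 0.559.
- 126/0.559 = 225.5, so 226; 226/0.95 = 237.9, so 238.

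This reproduces 226 and 238 exactly. Neither depends on treatment failure.

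**2. The two rules side by side.**

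| Participant's history after randomisation | Protocol 3.3.2.1 and SAP bullet | SAP derivation |
|---|---|---|
| Community steroids or antibiotics only | Event, at that date | 0, censored |
| Respiratory step-up without recorded intensification | Event, at that date | 0, censored |
| Death without both other components | Event, by date of death at the latest | 0, censored |
| Intensification, later a respiratory readmission | Event at intensification | Event at readmission |
| None of the three | Censored | Censored |

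With the same follow-up, every event under the SAP rule is also an event under the protocol rule, dated no earlier. The derivation can therefore only lose or delay events.

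**3. A size from the documents' own figures.** Protocol 10.1 says 6% of discharged patients died within 12 months without readmission. If that held in both arms, 0.06 × 226 = 13.6, about 14 participants. All are protocol failures. Without a readmission they could meet the SAP rule only through escalation during the index stay.

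**4. Illustration on assumed rates.** Assumed control arm: 1.2 community intensification courses a year, 55% with step-up by week 48, 12% mortality by week 48, 90% of step-ups accompanied by intensification, exponential times, hazard ratio 0.7 on every component, 119 per arm, full follow-up. Protocol 9.4 gives a 12% mortality without a time horizon, so applying it to 48 weeks is itself an assumption.

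Cumulative hazards to week 48:
- intensification I = 1.2 × 48/52 = 1.108
- step-up S = −ln 0.45 = 0.799
- death D = −ln 0.88 = 0.128
- sum = 2.034

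*Any of three:*
- control 1 − e^(−2.034) = 0.869; mepolizumab 1 − e^(−0.7 × 2.034) = 0.759
- events: 119 × (0.869 + 0.759) ≈ 194
- control median: 48 × ln 2/2.034 ≈ 16 weeks

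*Both, later date, before death.* Let F(a) = a/(a + D) × [1 − e^(−(a + D))], the probability that an event with hazard a occurs by week 48 and before death.
- Step-up with intensification (90%): F(S) = 0.521.
- Step-up without it (10%): F(I) + F(S) − F(I + S) = 0.342.
- Control: 0.9 × 0.521 + 0.1 × 0.342 = 0.503.
- Mepolizumab, all hazards × 0.7: 0.9 × 0.411 + 0.1 × 0.219 = 0.392.
- Events: 119 × (0.503 + 0.392) ≈ 106.
- By simulation, the control median with deaths censored is about 44 weeks, and about 71% of control deaths are never counted.

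SE(log HR) = 2/√events: 2/√194 = 0.144 against 2/√106 = 0.194, a rise of about 35%.

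**5. Range.**
- Overlap held at 90%, community courses 0.4 to 2 a year, step-up 40% to 65%, death 6% to 12%: SE rises by about 16% to 63%.
- Other inputs as in step 4, overlap varied from 100% down to 0: about 32% to 70%.
- A separate grid with no built-in overlap (113 per arm; control intensification 40% to 80%, step-up 30% to 60%, death 12%; hazard ratio 0.6 on the non-fatal components and 1 on death; independent or shared-frailty times) gives about 112 to 196 events under any-of-three and 17 to 101 under the SAP rule. Its mildest case is 183 against 101, √(183/101) = 1.35. Its most extreme is 125 against 17, √(125/17) = 2.71. That extreme overstates the loss if readmissions usually bring steroids or antibiotics.

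**The case against.** The strongest reply is that the SAP states the correct composite directly above the faulty paragraph, so a careful programmer might follow that and no harm would result. It is true that the SAP contradicts itself as well as the protocol, and which rule would be coded is unknown. But the derivation is the operational instruction. It is not a one-word slip either: reading *latter* as *earlier* would still leave the next sentence requiring both components, and neither sentence mentions death. Nor is it a declared change. Where the SAP departs from the protocol on the log-rank test (6.4.1) it says so in the text, and here it does not.

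Other points stand in part. This is a secondary outcome and is not among the key secondary outcomes that SAP 6.5.3 singles out for sensitivity analysis. Deaths are not lost from the report, because all-cause death and the primary composite are analysed separately. The illustration rests on rates and an overlap the documents do not give, and it ignores truncated follow-up, so the 35% should be read only with its range. An earliest-date rule also needs care, because consent and randomisation can take place during the index stay (Protocol 7.2) while treatment of the index exacerbation continues. None of this rescues the rule as written.

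**Conclusion.** The concern holds. The SAP's derivation of treatment failure contradicts the protocol and the SAP's own definition in logic, date and use of death, and the change is undeclared. That conclusion rests on the text alone.

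The size is less certain. About 14 of 226 participants would be affected through death without readmission, if the protocol's 6% applied in both arms. On assumed rates that include overlap between readmission and intensification, the standard error rises by roughly 16% to 70%. Only the exact size depends on those assumptions: the SAP rule cannot add events or bring any forward. The effect on the hazard ratio itself cannot be predicted from the documents.

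It must be corrected before database lock, since the trial would otherwise report a prespecified endpoint under the wrong definition. The primary analysis and the 226/238 sample size stand.

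**What to change.** Replace the derivation in SAP 3.2.1 so that:

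- the event date is the earliest of (a) the first systemic corticosteroid or antibiotic intensification for respiratory reasons, (b) the first respiratory step-up in hospital care or readmission, and (c) death from any cause, each counted from randomisation;
- the indicator is 1 if any of the three occurs;
- only participants with none of the three are censored, at the last assessment known to be free of all three.

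In the same edit, state how intensification or step-up is identified as new for participants randomised while still in hospital for the index exacerbation.

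The core correction is two sentences of SAP wording and a small change to the derivation code. The first-event rule restores the protocol's own definition. It needs no new type of data and changes no trial conduct.
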